Clinical Laboratory Assessment Value Changes: It is the investigator's or subinvestigator's responsibility to review the results of all laboratory tests as they become available. This review will be documented by the investigator's or subinvestigator's dated signature on the laboratory report. For each abnormal laboratory test result, the investigator or subinvestigator needs to verify whether this is an abnormal (ie, clinically relevant) change from baseline for that individual subject. This determination, however, does not necessarily need to be made the first time an abnormal value is observed. The investigator or subinvestigator may repeat the laboratory test or request additional tests to verify the results of the original laboratory tests. If this laboratory value is considered clinically relevant by the investigator or subinvestigator (eg, subject is symptomatic, requiring corrective treatment or further evaluation), or if the laboratory value leads to discontinuation or meets the criteria for an SAE, this is considered an AE.

Severity: Adverse events will be graded on a 3-point scale and reported as indicated on the eCRF. The intensity of an AE is defined as follows:

- 1 = Mild: Discomfort noticed, but no disruption to daily activity.
- 2 = Moderate: Discomfort sufficient to reduce or affect normal daily activity.
- 3 = Severe: Inability to work or perform normal daily activity.

IMP Causality: Assessment of causal relationship of an AE to the use of IMP is defined as follows:

Related: There is a reasonable possibility of a temporal and causal relationship between the IMP and the AE.

Not related: There is no temporal or causal relationship between the IMP and the AE.

Date of Onset and Recovery (for diarrhea and vomiting, date and time of onset and date and time of recovery):

Date of onset: The date of onset of an AE or date of confirmation of an AE. If the severity or seriousness of the reported event changes, the date of exacerbation will be taken as the "date of onset of AE."

Date of recovery: The date of recovery of an AE or date of confirmation of recovery of an AE. For clinical laboratory items, this shall be the date of blood or urine sampling. In the case of death, this shall be the date of death.

Outcome:

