The outcome of an AE will be selected from the following 6 categories (one only). If the subject died, the date of death will be recorded; if the subject's condition was ameliorated (recovering), unrecovered, or unknown, the date of outcome confirmation will be recorded.

- Recovered
- Ameliorated (recovering)
- Unrecovered
- Recovered but with sequelae
- Death
- Unknown (for some reason, a follow-up investigation could not be performed even once)

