5.2 Eliciting and Reporting Adverse Events

The investigator or subinvestigator will periodically assess subjects for the occurrence of AEs. To avoid bias in eliciting AEs, subjects should be asked the nonleading question: "How have you felt since your last visit?" All AEs (serious and nonserious) reported by the subject must be recorded on the source documents and eCRFs provided by the sponsor. The name of an AE, date of onset, date of recovery, seriousness, severity, causal relationship to the IMP, and outcome will be recorded on the source documents and eCRF.

Adverse event and SAE collection is to begin after a subject has signed the ICF and continue until the end of trial date. Adverse events occurring in the screening period and Period 1 will be assessed in comparison with the subject's condition at the time of consent/screening, and AEs occurring in Period 2 and Period 3 (Cohort 1 and Cohort 1' (as necessary) [single administration period] only) will be assessed in comparison with the subject's condition at the start of Period 2. For subjects who were withdrawn from the

trial at the discretion of the sponsor and resume participation in the trial from Period 2 or 3, AEs and SAEs will be collected from the time participation in the trial resumes until the end of the trial. However, AEs that occur after withdrawal from the trial at the discretion of the sponsor and resolve before the date on which the subject provided his/her signature for re-consent will also be collected as far as possible. Adverse events will be assessed based on the following:

- Subjects who resume participation in the trial from Period 2: Adverse events occurring in the screening period will be assessed in comparison with their condition at the time of consent/screening when they first participated in the trial, and AEs occurring in Period 2 and Period 3 will be assessed in comparison with their condition prior to IMP administration in Period 2.
- Subjects who resume participation in the trial from Period 3: Adverse events occurring in the screening period and Period 3 will be assessed in comparison with their condition at the start of Period 2 when they first participated in the trial.

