Use medical terminology in AE reporting. Adverse events should be reported as a single unifying diagnosis whenever possible or, in the absence of a unifying diagnosis, as individual signs or symptoms. Exacerbation or disease progression should be reported as an AE only if there are unusual or severe clinical features that were not present, or experienced earlier, or not expected based on the course of the condition.

A reported AE that undergoes a change in severity or seriousness must be reported as a new AE on the eCRF.

In addition, the sponsor must be notified immediately by e-mail of any IREs according to the procedure outlined below, in Section 5.3 Immediately Reportable Events. Special attention should be paid to recording hospitalization and concomitant medications.

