7.6 Protocol Deviations

A listing of major protocol deviations will be presented.

8 Efficacy Analysis

Not applicable.

9 Safety Analyses

Each safety endpoint will be summarized for each dose (Periods 2 and 3) of the QW formulation in the single administration period (Cohort 1 and Cohort 1' [as necessary]) and for the repeated administration period (Cohort 2) based on safety analysis set.

The baseline for statistical analysis is defined as data measured immediately prior to IMP administration in Period 2.

Adverse events (AEs) in each period are defined as AEs occurred on or after the IMP administration in each period to before the IMP administration in next period or the end of study.

Potentially clinically significant (potentially clinically significance [PCS]) abnormalities in each period will include the values measured on or after the IMP administration in each period to before the IMP administration in next period or the end of study.

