9.2 Adverse Events

All AEs will be coded by system organ class (SOC) and Medical Dictionary for Regulatory Activities (MedDRA version 23.1) preferred term (PT). If multiple occurrences of the same event are observed in the same subject during the same period, the highest severity will be used for analysis. The incidence of the following events will be summarized by SOC and PT:

- AEs occurring after administration of the QW formulation (treatment-emergent adverse events [TEAEs])
- TEAEs by severity
- TEAEs with an outcome of death
- Serious TEAEs
- TEAEs leading to discontinuations of the trial
- TEAEs by onset time (1-7 and 8-14 for Cohort 1 and Cohort 1' [as necessary]; 1-7 8-14, 15-21, 22-28, 29-35, 36-42 for Cohort 2)

The above summaries will also be prepared for TEAEs potentially causally related to the IMP.

Incidences of the AEs occurring in period 1 will be summarized by SOC and PT for subjects treated with conventional tablet.

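### Read literally, Protocol 5.2 turns an improving adverse event into a new AE with no defined onset date, so a Period 2 event that eases after the Period 3 dose can be counted against the higher dose

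*Protocol*

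**What the plan says.** **Recording.** Protocol Section 5.2 states: "A reported AE that undergoes a change in severity or seriousness must be reported as a new AE on the eCRF". It is mandatory and gives no direction. It also requires an onset date for every AE.

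**Onset date.** Protocol Section 5.1 uses the same trigger but speaks only of worsening: "If the severity or seriousness of the reported event changes, the date of exacerbation will be taken as the" date of onset. It gives no onset date for an improvement.

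**Outcome.** The outcome list in Section 5.1 has a category for an event that is getting better, "ameliorated (recovering"), entered on the existing record with the date the outcome was confirmed.

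**Reference state.** Under Section 5.2, AEs in Periods 2 and 3 "will be assessed in comparison with the subject's condition at the start of Period 2".

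**Analysis.** SAP Section 9 assigns events to a period as "AEs occurred on or after the IMP administration in each period to before the IMP administration in next period or the end of study". SAP Section 9.2 defines the treatment-emergent set as "AEs occurring after administration of the QW formulation (treatment-emergent adverse events [TEAEs"]). If the same event recurs in one subject within one period, the highest severity is analysed. The listed summaries include "TEAEs by onset time (1-7 and 8-14 for Cohort 1" and Cohort 1', and six weekly bins to Day 42 for Cohort 2. No SAP rule links a continuation record to the event it continues.

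**The concern.** Safety is summarised by QW dose, so whether an event belongs to 24 mg or 48 mg is central to the tolerability results of Cohort 1. A site that follows Section 5.2 literally must open a new record when a moderate event becomes mild, and must enter an onset date for it. The protocol does not say which date. If the site enters the date of the improvement, and that date falls after the Period 3 dose, a fading 24 mg event becomes a 48 mg TEAE.

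In Cohort 2 the matter concerns timing. Protocol Section 2.3.1 justifies the low first dose by the possibility of AEs soon after therapy starts, and the onset-week table is where that pattern would show. If a resolving event is entered as a fresh onset each time it eases, early events spread into later weeks. With approximately 20 sites, inconsistent entry is a realistic risk.

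**Working it through.** The documents give no figure to reproduce on this point. The check follows the counting rules through simple cases.

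**Inputs**
- New-record rule and reference state: Protocol 5.2.
- Onset date, three severity grades, outcome categories: Protocol 5.1.
- Period assignment: SAP 9. Within-period rule and onset bins: SAP 9.2.
- Interval between the Period 2 and Period 3 doses: at least 27 days (Protocol 3.1.1).
- Target of 20 completers per cohort: Protocol 3.3.1.1.

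**1. Cohort 1, Period 2 to Period 3.** Take an event that is absent at the start of Period 2, moderate after 24 mg, still moderate at the 48 mg dose and mild some days later. Assume that the date of improvement is entered as onset.
- Reference state: mild is still worse than absent, so the new record qualifies as a Period 3 AE.
- Period assignment: the record is dated after the Period 3 dose, so it belongs to Period 3.
- Highest-severity rule: the two records lie in different periods, so they are not collapsed.
- Result: 1 count in Period 2 and 1 in Period 3. If only worsening opens a record, the result is 1 and 0.

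**2. Period 1 to Period 2.** A Period 1 event that eases after the first QW dose is better than the condition at the start of Period 2. Under Section 5.2 it should not be a new Period 2 AE. This route is closed.

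**3. Cohort 2, overall incidence.** All five QW doses are in Period 2. A severe, moderate, mild sequence gives three records, but the subject is counted once, at severe. There is no inflation.

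**4. Cohort 2, onset-week table.** Records on Days 3, 10 and 17, same preferred term:

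| Course | Entry rule | Records | Bins if counted once per bin | Bin if only the highest-severity record is kept |
|---|---|---|---|---|
| Severe, moderate, mild | Every change | 3 | 1-7, 8-14, 15-21 | 1-7 |
| Severe, moderate, mild | Worsening only | 1 | 1-7 | 1-7 |
| Mild, moderate, severe | Every change | 3 | 1-7, 8-14, 15-21 | 15-21 |
| Mild, moderate, severe | Worsening only | 3 | 1-7, 8-14, 15-21 | 15-21 |

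The SAP does not say which of the last two columns applies. A severe IMP-related event on Day 3 would normally lead to withdrawal before the Day 8 dose (Protocol 3.9.3.2), so the first course is an extreme case. A moderate event on Day 3 that becomes mild on Day 10 shows the same effect on a smaller scale: two records, filling bins 1-7 and 8-14 on one reading and bin 1-7 alone on the other.

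**5. Scale.** 1/20 × 100 = 5 percentage points per recounted subject in a cell.

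**The case against.** The strongest reply is that Sections 5.1 and 5.2 should be read together. Both start from a change in severity or seriousness, and 5.1 then speaks only of exacerbation. The recovering outcome gives improvement its own place. On that reading only worsening opens a new AE and nothing is recounted. This is a reasonable reading and may be what was intended. It does not remove the problem, because 5.2 is mandatory and undirected, and the eCRF completion instructions are not among the documents. The conflict is therefore unresolved, and it would be too strong to infer that every improving event will be entered as a new onset.

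Three further limits stand.
- The highest-severity rule in SAP 9.2 is stated ahead of the whole list of summaries, including the onset table. If it governs that table, milder later records drop out. A reader might infer that resolving events necessarily spread across weeks; the SAP does not settle this.
- The Cohort 1 carry-over is narrow. The doses are at least 27 days apart, so an event that begins on the day of the 24 mg dose must last at least that long; one that begins later in Period 2 needs less. Severe IMP-related events within two weeks of the Period 2 dose normally lead to withdrawal.
- The trial is descriptive, and a subject-level AE listing (AE-1) is planned, so split records would be visible. A listing does not correct the incidence tables, however.

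**Conclusion.** The point holds as an inconsistency between Protocol 5.1 and 5.2, together with a missing counting rule in SAP 9 and 9.2. The firm consequence is that nothing in the plan prevents a Period 2 event that eases after the Period 3 dose from being counted as a TEAE of the higher dose. This assumes that the site follows 5.2 literally and enters the date of improvement as onset. The possible consequence is that a resolving event fills several onset-week bins in Cohort 2, if the highest-severity rule does not apply to that table.

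A reader might go further and infer that Cohort 2 incidence is inflated, or that Period 1 events leak into the QW counts. The within-period rule excludes the first, and the Section 5.2 reference state excludes the second.

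The figure of 5 percentage points is the scale of one recount, not an estimate of bias. It uses 20, which is a completer target; the safety set is everyone who received the QW formulation, so the denominator may be larger and the step slightly smaller. The documents give no frequency of severity changes, so the number of recounts cannot be estimated.

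**What to change.** **Protocol 5.1 and 5.2 (or the eCRF completion guide).** Word both sections alike: a new AE record is opened only when severity worsens or a non-serious event becomes serious, and the onset date of that record is the date of that change. Improvement is entered in the existing record and creates no new onset date.

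**SAP 9.2.** Add that a continuation record of the same event is linked to the event it continues when its severity is lower, or when its severity is equal and it has not become serious. A linked record is not a new TEAE or a new onset, across periods or in the onset-time tables. A record that becomes serious is still counted, even at unchanged severity. A rule that simply dropped every record of equal or lower severity would remove such an event from the serious-TEAE table of the dose after which it became serious. State also whether the highest-severity rule governs the onset-time tables.

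**Cost.** About one sentence in the protocol or completion guide, two or three in the SAP, and a programmed check for adjoining records with the same preferred term among those already entered. No new data are needed.

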5.3 Immediately Reportable Events

The investigator or subinvestigator must report any SAEs, AEs related to occupational exposure, potential serious hepatotoxicity, or confirmed pregnancy immediately after the investigator, subinvestigator, or designee becomes aware of the event. The IRE form and so on should be completed and sent by e-mail to the sponsor, using the contact information on the title page of this protocol. (Please note that the IRE form is a specific form provided by the sponsor and is NOT the AE eCRF.) Due consideration must be given to the subject's privacy when an IRE form is sent by e-mail, etc.

Subjects experiencing SAEs or IREs should be followed clinically as described in Section 5.7.2 Follow-up of Serious Adverse Events and Immediately Reportable Events. It is expected that the investigator or subinvestigator will provide or arrange appropriate

supportive care for the subject and will provide prompt updates on the subject's status to the sponsor.

5.4 Potential Serious Hepatotoxicity

For a subject who experiences an elevation in aspartate aminotransferase (AST) or alanine aminotransferase (ALT) that is ≥ 3 times the upper limit of normal (ULN), total bilirubin should also be evaluated. If the total bilirubin is ≥ 2 times the ULN, complete the IRE form and so on with all values listed and also report as an AE on the eCRF.

5.5 Pregnancy

Women of child-bearing potential are defined as female subjects for whom menstruation has started and who are not documented as sterile (ie, have had a bilateral oophorectomy and/or hysterectomy or who have been postmenopausal for at least 12 months).

For WOCBP and for men who are sexually active, there must be a documented agreement that the subject and/or their partner will take effective measures (ie, double barrier method) to prevent pregnancy during the course of the trial and for 30 days after the last dose of IMP. Unless the subject or their partner is sterile (ie, women who have had a bilateral oophorectomy and/or hysterectomy or who have been postmenopausal for at least 12 consecutive months; or men who have had a bilateral orchidectomy) or remains abstinent, 2 of the following precautions must be used: vasectomy, tubal ligation, intrauterine device, or condom (all methods approved or certified in Japan). Any single method of birth control, including vasectomy and tubal ligation, may fail, leading to pregnancy. The contraceptive method will be documented at each trial visit.

Before enrolling WOCBP in this clinical trial, investigators or subinvestigators must review the below guidelines about trial participation with all WOCBP. The topics should generally include:

- General information
- Informed consent form
- Pregnancy prevention information
- Drug interactions with hormonal contraceptives
- Contraceptives in current use
- Guidelines for the follow-up of a reported pregnancy

Before trial enrollment, WOCBP must be advised of the importance of avoiding pregnancy during trial participation and the potential risk factors for an unintentional pregnancy. The subject must sign an informed consent form stating that the above-mentioned risk factors and the consequences were discussed with her.

A urine and/or serum pregnancy test for hCG will be performed at screening on all WOCBP. If a urine test is performed and is positive, the investigator or subinvestigator will follow up with a confirmatory serum test.

During the trial, all WOCBP should be instructed to contact the investigator or subinvestigator immediately if they suspect they might be pregnant (eg, missed or late menstrual cycle).

If a subject is suspected to be pregnant before she receives IMP, the IMP administration must be withheld until the results of the pregnancy test are available. If the pregnancy is confirmed, the subject must not receive the IMP and must not be enrolled in the trial. If pregnancy is suspected while the subject is taking IMP, the IMP must be withheld immediately (if reasonable, taking into consideration any potential withdrawal risks) until the result of the serum pregnancy test is known. If pregnancy is confirmed, the IMP will be permanently discontinued in an appropriate manner (eg, dose tapering if necessary for subject safety) and the subject will be withdrawn from the trial.

The investigator or subinvestigator must immediately notify the sponsor of any pregnancy associated with IMP exposure during the trial and for 30 days after the last dose of IMP, and record the event on the IRE form and so on, and forward it to the sponsor. The sponsor will forward Pregnancy Surveillance Form(s) for monitoring the outcome of the pregnancy. This procedure also applies to the case where the partner of a subject becomes pregnant.

Protocol-required procedures for trial discontinuation and follow-up must be performed on the subject unless contraindicated by pregnancy (eg, x-ray studies). Other appropriate pregnancy follow-up procedures should be considered, if indicated. In addition, the investigator or subinvestigator must report to the sponsor, on appropriate Pregnancy Surveillance Form(s), follow-up information regarding the course of the pregnancy, including perinatal and neonatal outcome. Infants will be followed for a minimum of 6 months from the date of birth.

5.6 Procedure for Breaking the Blind

Not applicable.

5.7 Follow-up of Adverse Events

5.7.1 Follow-up of Nonserious Adverse Events

Nonserious AEs that are identified at any time during the trial must be recorded on the AE eCRF with the current status (ongoing or resolved/recovered) noted. All nonserious events (that are not IREs) that are ongoing at the end of trial date (final day of Confidential - Proprietary Information 90 Version 4.0, 18 Jun 2020

observation) will be recorded as ongoing on the eCRF. For any AE having been identified throughout the trial, during analysis, additional relevant medical history information may be requested by the sponsor to further ascertain causality (including, but not limited to, information such as risk-related behavior, family history and occupation). The follow-up information after the end of trial date (final day of observation) will be recorded in the subject's medical record.

5.7.2 Follow-up of Serious Adverse Events and Immediately Reportable Events

This trial requires that subjects be actively monitored for SAEs and IREs up to the end of trial date (final day of observation).

Serious AEs and IREs that are identified or ongoing at the end of trial date must be recorded on the AE eCRF page. Between the end of trial date for the individual subject and the end of trial date for the last subject, if any new information regarding an SAE or IRE becomes available (eg, the event is resolved), this must be reported to the sponsor using the IRE form and so on, and the information must be recorded on the AE eCRF page.

The investigator or subinvestigator will follow SAEs and IREs, and will continue to report any significant information to the sponsor until the events are resolved or stabilized, or the subject is lost to follow-up or has died, using the IRE form and so on.

Resolved means that the subject has returned to the baseline state of health, and stabilized means that the investigator or subinvestigator does not expect any further improvement or worsening of the subject's condition.

5.7.3 Follow-up and Reporting of Serious Adverse Events Occurring After the End of Trial Date (Final Day of Observation)

Any new SAEs or IREs reported to the investigator or subinvestigator, which occur after the end of trial date (final day of observation) and are determined by the investigator or subinvestigator to be associated with the use of the IMP, should be reported to the sponsor. This includes SAEs and IREs that are captured on follow-up telephone contact or at any other time point after the defined trial period. The investigator or subinvestigator will follow SAEs and IREs identified after the defined trial period and continue to report any significant follow-up information to the sponsor until the events are resolved or stabilized, or the subject is lost to follow-up or has died, using the IRE form and so on.

6 Pharmacokinetic/Pharmacodynamic/Pharmacogenomic Analysis

